3.2.2. Primary Endpoints

The primary effectiveness endpoint is Primary Patency at 12 months post-procedure. This will be estimated through 365 days along with a 95% confidence interval using Kaplan-Meier analysis.

The primary safety endpoint is procedure or device-related Serious Adverse Events within 30 days of the index procedure. The total number of events as well as the number of Subjects experiencing them will be tabulated along with a 95% confidence interval.

3.2.3. Secondary Endpoints

The secondary endpoints for this study include:

- Acute Procedural Success
- Primary Patency at 30 days, 12, 24 and 36 months
- Primary Assisted at 30 days, 12, 24 and 36 months
- Secondary Patency at 30 days, 12, 24 and 36 months
- Freedom from Target Lesion Revascularization at 30 days, 12, 24 and 36 months
- Freedom from Major Amputation at 30 days, 12, 24 and 36 months
- Change in Ankle-Brachial Index from pre-procedure at 30 days, 12, 24 and 36 months
- Change in Rutherford Category from pre-procedure at 30 days, 12, 24 and 36 months
- Stent Fracture Assessment at 12, 24 and 36 months

4. Study Population

4.1. Description of Population

Patients presenting with $\geq 50\%$ in-stent restenosis and/or an occlusion in a previously implanted non-covered stent(s) located in the superficial femoral artery are eligible for participation in the study. The previously implanted non-covered stent(s) must have been implanted greater than 30 days prior to the index procedure. Eligible patients must present with life-limiting claudication, resting leg pain or minor tissue loss (Rutherford Category 2-5). Patients must be candidates for endovascular treatment.

Patients presenting with the following lesion characteristics are eligible for enrollment:

- Total lesion length of up to 270 mm, consisting of in-stent and adjacent occlusive disease
- Reference vessel diameter between approximately 4.0 and 6.5 mm

The study has been designed with standard eligibility criteria to address any known or foreseeable factors that may compromise the outcome of the study or the interpretation of results. Only patients who meet all of the Inclusion Criteria and none of the Exclusion Criteria will be enrolled.

4.2. Inclusion Criteria

Potential Subjects must meet all of the following Clinical Inclusion Criteria:

1. Patient is ≥ 18 years old at the time of informed consent signature
2. Patient is willing to give written informed consent
3. Patient has a previously implanted (>30 days) non-covered stent(s) located in the superficial femoral artery
4. Patient has life-style limiting claudication, resting leg pain or minor tissue loss (Rutherford Category 2-5)
5. Patient demonstrates an ABI ≤ 0.9 . If ABI > 0.9 or not measureable, patient is eligible for study if toe-brachial index (TBI) is ≤ 0.5
6. Patient is male, infertile female or female of childbearing potential with a negative beta hCG pregnancy test within 7 days of the index procedure
7. Patient is capable of complying with protocol requirements, including follow-up visits

Potential Subjects must meet all of the following Angiographic Inclusion Criteria:

1. Patient has $\geq 50\%$ in-stent restenosis and/or an occlusion in a previously implanted (>30 days) non-covered stent(s) located in the superficial femoral artery defined as beginning at least 1 cm below the origin of the profunda femoris artery and ending at least 1 cm above the intercondylar notch
2. Patient has a maximum total lesion length of 270 mm, consisting of in-stent and adjacent occlusive disease
3. Patient has a minimum of 1 cm of non-stenosed vessel both proximal and distal to the target lesion(s)
4. Patient has a reference vessel diameter between 4.0 and 6.5 mm
5. The guidewire and delivery system must cross the target lesion(s) intraluminally
6. Patient has a patent popliteal artery ($<50\%$ stenosis) distal to the target vessel
7. Patient has at least 1 patent infrapopliteal runoff vessel ($<50\%$ stenosis) not requiring intervention

CONFIDENTIAL INFORMATION

MD133246 Protocol Template

Revision#: 1

Doc Type: GC

8. Angioplasty balloon can be fully expanded in the target lesion during pre-treatment step

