3.2. Study Endpoint(s)

3.2.1. Definitions

Ankle Brachial Index: the ankle systolic pressure in the study limb divided by the highest brachial systolic pressure in either arm

Acute Procedural Success: successful delivery of study device and complete coverage of the target lesion without a procedure or device-related Serious Adverse Event prior to hospital discharge

Major Amputation: removal of the lower limb above the metatarsals in the study limb, resulting from a vascular event

Patency: blood flow through the study device

Primary Patency: patent blood flow through the study device, which requires either a PSVR measurement ≤ 2.5 or patent flow indicated by the Core Lab, and without repeat intervention

Primary Assisted Patency: blood flow through the study device regardless of repeat interventions to maintain patency prior to occlusion

CONFIDENTIAL INFORMATION

MD133246 Protocol Template

Revision#: 1

Doc Type: GC

Secondary Patency: blood flow through the study device regardless of repeat interventions to maintain or restore patency after occlusion

Target Lesion(s): stenotic or occluded segment(s) within and adjacent to a previously implanted non-covered stent(s) (>30 days) in the superficial femoral artery. An adjacent lesion is an extension of the stenotic or occluded segment that is contiguous with that lesion within the previously implanted non-covered stent

Target Lesion Revascularization (TLR): repeat intervention within the study device and 5 mm proximal or distal to the edge of the study device to maintain or re-establish patency

Toe Brachial Index: the toe systolic pressure in the study limb divided by the highest brachial systolic pressure in either arm

Stent Integrity: freedom from study device stent fracture which is clearly distinguishable on imaging from the previously implanted non-covered stent

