5.4. Enrollment

The patient is considered enrolled when all inclusion criteria and no exclusion criteria have been met (as defined in Section 4.2 & 4.3).

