5.5. Procedure

Patients may be admitted the day prior to the procedure for hydration, if deemed medically necessary. Alternatively, Subjects may be admitted the day of the procedure. Antiplatelet medication should be initiated prior to placement of the study device at a dose deemed appropriate by the Investigator.

On the day of the procedure, the patient will be prepped for percutaneous intervention per institutional standards. Ultrasound-guided vascular access is recommended. When possible, a percutaneous Seldinger technique is preferred; however a cut-down may be performed when indicated. The guidewire must cross the target lesion(s) intraluminally. Use of image-centered, magnified-view contrast angiography (including a marker guidewire or catheter) is recommended.

Assessment of Lesion Characteristics

Procedural angiography will be utilized to assess target lesion characteristics and to determine final eligibility for enrollment. Lesion characteristics, including total lesion length, percent stenosis, presence of occlusion and calcification will be recorded.

Additionally, target lesion location should be recorded, confirming the presence of in-stent restenosis and noting any adjacent disease (if present).

CONFIDENTIAL INFORMATION

MD133246 Protocol Template

Revision#: 1

Doc Type: GC

Assessment of Non-covered Stent

A baseline image of the previously implanted non-covered stent prior to any study treatment is required. This image can be captured during the baseline angiogram (X-ray shot without contrast) or by plain film X-ray. Imaging will be sent to the Core Lab for assessment.

Treatment of Target Lesion and Device Deployment

Prior to study device implantation, pre-dilation of the target lesion is required with full expansion of the balloon within the lesion(s). The margins of the angioplasty treatment should be carefully marked to ensure complete coverage with the study device. The results of the pre-dilation should be evaluated angiographically. Any other pre-treatment procedures prior to balloon angioplasty may be conducted at the discretion of the Investigator.

Study device sizing, introduction, positioning and deployment should be performed in compliance with Instructions for Use (IFU). Refer to **Table 1**, GORE® VIABAHN® Endoprosthesis Configurations and Vessel Sizing Guidelines.

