10.2. Secondary Endpoint Analysis

10.2.1. Acute Procedural Success

Acute Procedural Success is defined as successful delivery of the study device and complete coverage of the target lesion without a procedure or device-related Serious Adverse Event prior to hospital discharge. This will be tabulated omitting all Subjects with unknown status.

CONFIDENTIAL INFORMATION

MD133246 Protocol Template

Revision#: 1

Doc Type: GC

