10.6.2. Analysis Populations

Both of the following populations will be used for analyses of primary and secondary endpoints.

- (1) Intent to treat – All patients assigned to the study treatment, regardless of whether or not they received it or have any protocol violations.
- (2) Per protocol – A subset of the ITT population consisting of Subjects receiving the study device which meet all inclusion and exclusion criteria and without any major protocol violations.

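### Read literally, angiographic inclusion criterion 5 keeps a patient whose lesion the delivery system fails to cross from being enrolled, so this one type of delivery failure is missing from Acute Procedural Success and from ITT

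*Protocol*

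**What the plan says.** Angiographic inclusion criterion 5 in Protocol 4.2 reads "The guidewire and delivery system must cross the target lesion(s) intraluminally". Section 4.1 states "Only patients who meet all of the Inclusion Criteria and none of the Exclusion Criteria will be enrolled", and Section 5.4 uses the same condition to define enrolment: "The patient is considered enrolled when all inclusion criteria and no exclusion criteria have been met".

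Section 5.5 describes the procedure. On crossing it says "The guidewire must cross the target lesion(s) intraluminally" and does not mention the delivery system. It uses procedural angiography to settle final eligibility, and describes that step before pre-dilation and device deployment. It also has adverse events collected from the study procedure onward. Section 9.1.3 starts adverse event reporting at enrolment, after the final angiographic eligibility assessment.

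Section 3.2.1 defines Acute Procedural Success as "successful delivery of study device and complete coverage of the target lesion without a procedure or device-related Serious Adverse Event prior to hospital discharge". On the denominator, Section 10.2.1 says "This will be tabulated omitting all Subjects with unknown status". ITT in Section 10.6.2, repeated in SAP 5.2, is "All patients assigned to the study treatment, regardless of whether or not they received it or have any protocol violations". SAP 5.5.1 applies Acute Procedural Success to both ITT and per-protocol sets, with decision rules that are not visible in the public text.

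**The concern.** Whether the delivery system crosses the lesion can be learned only by advancing the study device. Criterion 5 therefore tests, as a condition of entry, part of what the first component of Acute Procedural Success is meant to measure. A patient who fails that test has had the device attempted, yet a site following Sections 4.1 and 5.4 would record a screen failure.

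Two things are at stake. The reported success rate would not respond to how often the delivery system fails to cross a restenosed stent. And because Section 9.1.3 ties adverse event reporting to enrolment, a serious event caused by the failed attempt might never reach the primary 30-day safety endpoint.

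**Working it through.** **Tracing one patient.** Take a patient who meets every other criterion. The guidewire crosses, pre-dilation is complete, the device is introduced, and the delivery system does not cross.

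1. Criterion 5 (4.2) is not met.
2. Under 4.1 and 5.4 the patient is not enrolled.
3. ITT (10.6.2; SAP 5.2) consists of patients assigned to treatment. The visible text of this single-arm study defines no act of assignment apart from enrolment, so the patient is not in ITT.
4. Acute Procedural Success is computed on ITT and per-protocol sets (SAP 5.5.1). The patient is in neither numerator nor denominator.
5. Under 9.1.3, adverse event reporting has not begun. Under 5.5, it has.

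Now follow 5.5 and 9.1.3 instead. Eligibility is settled at angiography, before the device is introduced, so the patient is enrolled and in ITT. The failed crossing is then a procedural failure, and the patient leaves only the per-protocol set. The same event has two classifications, depending on which section a site works from.

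**Illustrating the size.** The documents state no figure for Acute Procedural Success and no crossing-failure rate, so there is no figure to reproduce. The only document input is the planned enrolment of 108 (Protocol 3.1). The number of crossing failures, k, is assumed. Non-enrolled patients are replaced until 108 are enrolled, so the number attempted is 108 + k. With s successes among the 108:

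- reported rate = s / 108
- rate among attempted patients = s / (108 + k)

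With no other failures (s = 108) and exact (Clopper-Pearson) 95% intervals:

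| Crossing failures k (assumed) | Reported, as written | Among attempted |
|---|---|---|
| 1 | 108/108 = 100% (96.6 to 100) | 108/109 = 99.1% (95.0 to 100.0) |
| 2 | 100% | 108/110 = 98.2% (93.6 to 99.8) |
| 3 | 100% | 108/111 = 97.3% (92.3 to 99.4) |
| 5 | 100% | 108/113 = 95.6% (90.0 to 98.5) |

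The reported column is the same for every k. Other failures lower both columns without removing the gap. With three failures of other kinds among the 108 and k = 5, the reported rate is 105/108 = 97.2% and the rate among attempted patients is 105/113 = 92.9%.

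**The case against.** The strongest reply is that exclusion is not proven. ITT is worded to keep patients who did not receive the device, and the per-protocol set is a subset that received it and met all criteria. The plan evidently expects some ITT members to fail one or the other. Together with the sequence in 5.5 and 9.1.3, this supports a reading in which enrolment precedes device introduction and a crossing failure stays in ITT. That reading is available, so it would go too far to say that these failures can never count. But 4.1 and 5.4 make no exception for criterion 5, so the conflict remains.

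The guidewire sentence in 5.5 does not exclude a further requirement, and criterion 5 might be meant only to govern the route. Both points are fair. They make the text ambiguous rather than plainly contradictory, and sites would still have to guess.

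The decision rules in SAP 5.5.1 are not visible and might address the case. They are, however, stated to apply to the ITT and per-protocol sets, and so operate after those sets are formed.

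A reader might infer more than the documents support:

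- *That all delivery failures disappear, or that crossing failure is the main kind.* Deployment failure, incomplete coverage and related serious events before discharge arise in enrolled subjects and still count. Nothing in the documents ranks the kinds of failure.
- *That the comparison with RELINE is made more favourable.* The RELINE eligibility rules are not visible in the documents, and Protocol 10.1.1 places that comparison under primary patency. No direction can be claimed.

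Criterion 8, full balloon expansion at pre-treatment, already screens out some difficult lesions. The additional effect of criterion 5 after that step is unknown. Finally, consented patients go on the Screening and Enrollment Log (5.3), so crossing failures may be traceable, but no visible analysis uses the log.

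**Conclusion.** The point holds in a limited form. On the literal text of 4.1, 4.2 and 5.4, a failure of the delivery system to cross is removed before the Acute Procedural Success denominator and ITT are formed. Sections 5.5 and 9.1.3 allow another reading, so handling may differ between sites. For primary safety, the risk is that a serious event during a failed crossing goes uncounted; the conflicting starting points leave this open rather than certain.

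On the assumed range of 1 to 5 replaced failures with no others, the reported rate exceeds the rate among attempted patients by 0.9 to 4.4 percentage points (100 − 99.1; 100 − 95.6). The true size is unknown. Acute Procedural Success is a secondary endpoint that is only tabulated in the visible text, so no error rate or power is at issue. The change is still worth making, because a stated rule removes one type of failure from an endpoint meant to record it.

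**What to change.** - Reconcile criterion 5 in 4.2 with the crossing sentence in 5.5, so that eligibility does not depend on the study device having crossed the lesion.
- State in 5.4 that a patient who meets the other criteria is enrolled, and belongs to ITT, when introduction of the study device is first attempted. Refer to that moment in 10.6.2 and SAP 5.2.
- Align the start of adverse event collection in 5.5 and 9.1.3 with that moment.
- Count failure of the delivery system to cross as an Acute Procedural Success failure in ITT and report the number. State this in Protocol 10.2.1, and in SAP 5.5.1 unless its non-public rules already do so.

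The cost is a change of wording, with no added visits or tests. The reported success rate may be slightly lower, and a few enrolled subjects will have no device.

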4.3. Exclusion Criteria

Potential Subjects will not be eligible for study participation if they meet any of the following Clinical Exclusion Criteria:

1. Patient has a known allergy to stent graft components (nickel-titanium or ePTFE)
2. Patient has known allergy to contrast media that cannot be adequately pre-medicated prior to the study procedure
3. Patient with known hypersensitivity to heparin, including those patients who have had a previous incidence of heparin-induced thrombocytopenia (HIT) type II
4. Patient has a known intolerance to anticoagulation or antiplatelet therapy
5. Patient has an uncorrected bleeding disorder (platelet count <80,000/ μ L)
6. Patient has any known coagulation disorder, including hypercoagulability
7. Patient has severe chronic renal insufficiency (creatinine level \geq 2.5mg/dL) within 30 days prior to study procedure unless currently on hemodialysis
8. Patient has septicemia or uncontrolled infection
9. Patient has any planned surgical intervention/procedure within 30 days of the study procedure
10. Patient has major distal amputation (above the transmetatarsals) in the study or non-study limb
11. Patient has prior ipsilateral femoral artery bypass
12. Patient has severe medical comorbidities (untreated CAD/CHF, severe COPD, metastatic malignancy, dementia, etc.) or other medical condition that would preclude compliance with the study protocol or 3-year life expectancy
13. Patient has severe ipsilateral common or deep femoral disease requiring intervention
14. Patient has any previous surgery in the target vessel
15. Patient has had vascular access via the lower extremities within 30 days of the index procedure
16. Patient has had previous target vessel in-stent restenosis treated by relining with another stent
17. Patient is currently participating in another clinical research trial, unless approved by Sponsor

Potential Subjects will not be eligible for study participation if they meet any of the following Angiographic Exclusion Criteria:

1. Patient has untreated flow-limiting aortoiliac stenotic disease
2. Patient has an aneurysm adjacent to the target lesion(s)
3. Patient has perioperative unsuccessful ipsilateral percutaneous vascular procedure to treat inflow prior to enrollment during the index study procedure
4. Patient has femoral or popliteal aneurysm located in the target vessel
5. Patient has non-atherosclerotic disease resulting in occlusion (e.g. embolism, Buerger's disease, vasculitis)
6. Patient has angiographic evidence of intra-arterial thrombus or atheroembolism from inflow treatment
7. Patient has target lesion access not performed by transfemoral approach

CONFIDENTIAL INFORMATION

MD133246 Protocol Template

Revision#: 1

Doc Type: GC

5. Study Procedures/Evaluations

Any Site staff performing study-specific duties must be qualified by training and experience and must also be appropriately trained on the study protocol and procedures. Delegation of study-specific duties at each Site must be acknowledged by the Site's Principal Investigator and documented on the Delegation of Authority Log.

5.1. Schedule of Events

Table 3: Schedule of Events

	Pre-Procedure ¹	Procedure	Discharge	Follow-Up Visit		
				30 Days	12, 24 & 36 Months	Unscheduled
Informed Consent	X					
Medical History and Demographics	X					
Height and Weight	X					
CBC	X					
Creatinine, serum	X					
beta-hCG test, if indicated	X within 7 days of study procedure					
ABI/TBI, resting ²	X		X	X	X	X
Rutherford Classification	X			X	X	X
Anti-Platelet/Anti-Coagulation Therapy Assessment	X		X	X	X	X
Clinical Inclusion/Exclusion	X					
Angiography		X		If indicated	If indicated	If indicated
Angiographic Inclusion/Exclusion		X				
Adverse Events	X	X	X	X		X
X-Ray ³	X ⁴				X	
Duplex Ultrasound ³				X	X	If indicated

1 Pre-procedure assessments required within 30 days of study procedure unless noted

2 If TBI used to qualify patient for study participation, TBI must be collected throughout duration of all study follow-up intervals.

3 Imaging sent to Core Lab for Assessment

4 Required imaging: X-ray image of non-covered stent(s) prior to deployment of Study Device AND X-ray image of Study Device post-deployment

5.2. Informed Consent Process

All patients must provide informed consent prior to any study related procedures being performed. The case history (i.e., source documents/Subject chart) for each Subject shall document that such informed consent was obtained. The current IRB/EC approved consent form will be signed and personally dated by the Subject, and the person who conducted the informed consent discussion. The original signed informed consent form will be retained in the Subject records. A copy of the informed consent document will be given to the Subject for their records.

CONFIDENTIAL INFORMATION

MD133246 Protocol Template

Revision#: 1

Doc Type: GC

5.3. Pre-Screening/Screening

Patients who appear to meet clinical eligibility criteria via initial screening and review of existing medical records will be scheduled for a clinical evaluation. The informed consent must be signed prior to any study-related activity or procedure. All patients who sign an ICF will be considered entered into the screening phase of the study and should be recorded on the Screening and Enrollment Log.

The clinical evaluation must be performed within 30 days prior to the study procedure, unless noted, and will include:

- Informed consent
- Medical history and demographics
- Height and weight
- CBC
- Creatinine, serum
- b (beta)-hCG pregnancy testing within 7 days of the study procedure, if indicated
- ABI/TBI, resting (Note: If TBI is used to qualify patient for study participation, TBI must be collected throughout duration of all study follow-up intervals)
- Rutherford Classification
- Anti-platelet/anti-coagulation therapy assessment
- Review of clinical inclusion and exclusion criteria

5.4. Enrollment

The patient is considered enrolled when all inclusion criteria and no exclusion criteria have been met (as defined in Section 4.2 & 4.3).

